3.1.2 Secondary Endpoints

The secondary endpoints of this study are the:

- 1. Total annualized bleeding rate (TABR)
 - TABR will be calculated as the total number of BEs in the time period between first dose of IMP and the Study Completion Visit, divided by the duration (in years) between first dose of IMP and the Study Completion Visit. Surgery periods, and BEs occurring within these periods, will be excluded from the calculation of TABR.
- 2. Spontaneous annualized bleeding rate (SABR), calculated in analogy with TABR
- 3. Efficacy of *Wilate* in the treatment of breakthrough BEs based on the proportion of BEs successfully treated with *Wilate*
- 4. Wilate consumption data (FVIII IU/kg per week per patient) for prophylaxis
- 5. Incremental IVR of *Wilate* over time (at baseline, and at 3 and 6 months of treatment)
- 6. Association between AB0 blood type and the FVIII:C half-life of Wilate
- 7. Association between VWF:Ag concentration and the FVIII:C half-life of Wilate
- 8. Safety and tolerability of *Wilate* by monitoring adverse events (AEs) throughout the study
- 9. Immunogenicity of *Wilate* by testing for FVIII inhibitors
- 10. Virus safety in terms of parvovirus B19

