5.4 Dose and Dosing Schedule

5.4.1 PK Assessment Phase

In the 2-day PK Assessment Phase performed before the start of the Prophylactic Treatment Phase, *Wilate* will be administered to all patients as a single dose of 50 ± 5 IU kg BW.

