6.1.2 PK Visit

Patients will receive *Wilate* at a dose of 50 ± 5 IU/kg (labelled dose) after a washout period of at least 72 hours from their last FVIII injection. Patients must not be experiencing any bleeding.

The following assessments will be performed:

- Body weight before injection
- Blood samples will be taken for the following purposes and at the following time points:
 - FVIII:C plasma concentration (OS and CHR) for PK assessment within 1 h before injection and 15±5 min, 1 h (±5 min), 6 h (±30 min), 24±2 h, and 48±2 h after the end of injection
 - Safety laboratory before and 48±2 h after injection
 - **FVIII inhibitor** before injection
 - Plasma VWF:Ag and VWF:Ac within 1 h before injection and 15±5 min after the end of injection
- Vital signs before injection as well as 1 h (±5 min) and 48±2 h after injection
- AE monitoring
- Concomitant medications

At the end of this visit, patients will **receive a patient diary**. The Investigator will explain to the patient how to fill in the diary and emphasize the importance of carefully documenting all treatment details, AEs, and concomitant medications. Also, patients will be **provided with IMP** for home treatment. They will be re-supplied whenever necessary during the study.

The first prophylactic injection of *Wilate* after the PK Visit marks the beginning of the Prophylactic Treatment Phase.

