7.2.2 IMP Administration Data

The following parameters will be documented:

- Dates and times of IMP injections
- Doses of IMP in IU and IMP batch numbers
- Purpose of IMP injection (PK, IVR, prophylaxis, treatment of BE, surgery)

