5 STATISTICAL ANALYSES

All statistical analyses will be performed using SAS[®] for Windows (Version 9.3 or later).

Descriptive statistics will always be given for the entire population.

| | |
|---|---------------|
| 
STATISTICAL ANALYSIS PLAN Protocol No: WIL-30
 | |
| Version Number: 1.2 | Page 16 of 27 |
| Date of Issue: 2019-07-08 | |

The analysis of safety will be based on the SAF set.

Analysis of the PK properties of *Wilate* will be based on the PK set.

For secondary endpoints, FAS and PP analyses will be carried out, unless these analysis sets differ by no more than 1 patient from the FAS.

Analysis of the efficacy and safety of *Wilate* in surgeries will be based on the SURG set.

If not stated otherwise the following standard descriptive statistics will be presented:

Descriptive statistics for continuous data

Number of subjects (N), arithmetic mean, standard deviation (SD), minimum, lower quartile, median, upper quartile and maximum will be presented. Usually mean and quartiles will have 1 decimal more, SD 2 decimals more than the original values (as given with min, max); N has no decimals. These descriptive statistics will be determined for measured values and for differences to baseline.

Descriptive statistics for categorical data

Absolute frequencies (N) will be presented with 0, relative frequencies (%) with 1 decimal. For changes from baseline, shift tables may be generated.

Inferential statistics

If not stated otherwise all statistical tests will be performed as described in the corresponding sections below.

All p-values will be rounded to 4 decimals (p<0.0001 will be displayed, if the p-values are less than 0.0001). Statistical significance will be declared if the rounded p-value will be less than 0.05.

All confidence intervals (CI) will be derived two-sided and at a confidence probability of 1- α = 0.95.

Listings

All subject data will be listed by subject. Identification variable will be the subject ID (composed of study, center and subject number separated by a hyphen, e.g. '30-01-01'). Any derived data listed will also be stored permanently and will be calculated as outlined in section 8.1 of this SAP.

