5.7.2 Efficacy

All efficacy variables will be analyzed based on the FAS and additionally on the PP set, unless these analysis sets are identical.

Efficacy endpoints are:

- Efficacy of prophylactic treatment with *Wilate* based on the total annualized bleeding rate (TABR) as well as the spontaneous annualized bleeding rate (SABR)
- Efficacy of *Wilate* in the treatment of breakthrough BEs based on the proportion of BEs successfully treated with *Wilate* (successfully includes efficacy ratings assessed as either ‘excellent’ or ‘good’)
- *Wilate* consumption data (FVIII IU/kg per week and per month per subject) for prophylaxis
- Incremental IVR of *Wilate* over time (at baseline, and at 3 and 6 months of treatment) (refer to section 5.8)

Efficacy of Prophylactic Treatment with Wilate

The analysis of the efficacy of prophylactic treatment with *Wilate* will be statistically evaluated by presenting descriptive sampling statistics for the TABR and SABR, along with an exploratory 95% CI for the mean. TABR and SABR will be calculated as the total number of BEs or total number of spontaneous BEs, respectively, in the time period between first dose of IMP and the study completion visit, divided by the duration (in years) between first dose of IMP and the study completion visit. Surgery periods, and BEs occurring within these periods, will be excluded from the calculation of annual bleeding rates

Efficacy in the Treatment of Breakthrough BEs

To assess the hemostatic efficacy of *Wilate* in the treatment of breakthrough bleedings, a frequency distribution of all such BEs being successfully treated will be presented, along with an exploratory 95% CI.

Primarily, all obtained data on treatment characteristics (IMP dosages, frequencies, total consumption) and BEs (duration, frequency, efficacy assessment) will be described by providing summary statistics.

In general, the efficacy of bleeding episodes will also be presented by type (spontaneous, traumatic, postoperative, other), sites (nose, oral cavity, knee, ankle, elbow, arm, leg, intestinal and other. In addition, knee, ankle and elbow sites will be summarized as site ‘joint’) and severity (minor, moderate, major, life-threatening).

| | |
|--|---------------|
| STATISTICAL ANALYSIS PLAN Protocol No: WIL-30 | |
| Version Number: 1.2 | Page 20 of 27 |
| Date of Issue: 2019-07-08 | |

Analysis of Other Secondary Endpoints

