8 APPENDICES

8.1 Formulas for derived variables

| Variable | Description |
|---|--|
| Actual potency | Potency of IMP (IU) based on central laboratory measurements of FVIII content by two assay methods: CHR (chromogenic) and OS (one-stage). The analysis of PK and IVR assessment will be based on actual potencies |
| Durations between two dates | Later date minus earlier date plus 1, expressed in days. (Remark: Duration will be 1, if both dates are the same.) |
| Spontaneous annualized bleeding rate (SABR) | Number of spontaneous bleedings (excluding bleedings occurring in surgery periods) between first dose of IMP and Study Completion visit (or last dose of IMP in case completion visit not performed) / time under prophylaxis (days)/365.25 (see prophylactic treatment phase) |
| Total annualized bleeding rate (TABR) | Number of bleedings (excluding bleedings occurring in surgery periods) between first dose of IMP and Study Completion visit (or last dose of IMP in case completion visit not performed) / time under prophylaxis (days)/365.25 (see prophylactic treatment phase) |
| Surgery Phase | Last treatment for surgery – first treatment for surgery + 1 |
| Prophylactic treatment phase | Date of completion visit or date of last treatment with IMP in case completion visit not performed) – (date of first prophylactic treatment after the PK visit) + 1 – Surgery phases |
| Time in study | Date of study completion – date of screening +1 |

| STATISTICAL ANALYSIS PLAN Protocol No: WIL-30 | |
|--|---------------|
| Version Number: 1.2 | Page 25 of 27 |
| Date of Issue: 2019-07-08 | |

| Variable | Description |
|---|---|
| Time under treatment | Date of last treatment – date of first treatment + 1 (average drug consumption data will be calculated relative to time under treatment) |
| AUC | Area under the curve from baseline to infinity $AUC = \sum \left(\frac{(C_n + C_{n+1})}{2} \cdot \Delta t \right) + \frac{C_{last}}{K}$ (C_{last} is the last available measurement) |
| AUC _{norm} | AUC normalized for the administered dose |
| AUMC | Area under the moment curve (from baseline to infinity) $AUMC = \sum \left(\frac{(t_n \cdot C_n + t_{n+1} \cdot C_{n+1})}{2} \cdot \Delta t \right) + \frac{C_{last} \cdot t_{last}}{K^2} + \frac{C_{last}}{K}$ |
| CL | Clearance $CL = \frac{D}{AUC}$ where D is the actual dose administered (see remark above) |
| C ₀ | FVIII concentration before IMP administration |

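### SAP v1.2 section 8.1 counts bleeds for TABR and SABR from the first (PK) dose of IMP but divides by time from the first prophylactic dose, unlike SAP 5.7.2 and Protocol v02 section 3.1.2

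*SAP*

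**What the plan says.** SAP v1.2 section 8.1 defines TABR with the numerator "Number of bleedings (excluding bleedings occurring in surgery periods) between first dose of IMP and Study Completion visit". If there is no completion visit, the count ends at the last dose of IMP. SABR uses the same window, restricted to spontaneous bleeds. Both are divided by time under prophylaxis, with a pointer to the table row for the prophylactic treatment phase. That row runs to the completion visit, starts at the "date of first prophylactic treatment after the PK visit) + 1", and subtracts surgery phases.

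SAP v1.2 section 5.7.2 defines the same two rates differently. The count, again from the first dose of IMP, is "divided by the duration (in years) between first dose of IMP and the study completion visit". Protocol v02 section 3.1.2 agrees with 5.7.2: the count is "divided by the duration (in years) between first dose of IMP and the Study Completion Visit".

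The protocol separates the two start dates. Section 5.4.1 places the single PK dose "In the 2-day PK Assessment Phase performed before the start of the Prophylactic Treatment Phase", and section 6.1.2 says that the first prophylactic injection "after the PK Visit marks the beginning of the Prophylactic Treatment Phase". Until the PK Visit the child stays on his previous FVIII product (section 6.1.1), so the PK dose is the first dose of IMP.

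The Listings paragraph of SAP section 5 says that derived data listed "will be calculated as outlined in section 8.1 of this SAP". SAP 3.2 states that no deviations from the protocol are planned.

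**The concern.** An event rate needs its events and its time at risk to come from the same period. In 8.1 they do not: the count opens at the PK dose and the clock opens later, at the first prophylactic injection. The 8.1 rate therefore exceeds the Protocol v02 rate for every child with at least one counted bleed and a gap between the two doses. A child with no bleeds scores zero either way.

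TABR and SABR are the two measures of prophylactic efficacy, and they are summarized over about 10 children and over 5 per age group. The programmer has two definitions to choose from. The quality-control step in SAP section 6, which checks outputs for agreement with the SAP, cannot settle the choice because the SAP disagrees with itself. If 8.1 is programmed, the reported rates will not match the endpoint definition in 5.7.2 or in Protocol v02, and no departure will have been declared.

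**Working it through.** Neither document states a planned or expected bleeding rate, so there is no figure to reproduce. The check compares the definitions and then sizes the difference.

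**Start and end of each part**

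| Source | Count starts | Time starts | Both end |
|---|---|---|---|
| SAP v1.2, 8.1 | first dose of IMP | first prophylactic injection after the PK Visit | completion visit |
| SAP v1.2, 5.7.2 | first dose of IMP | first dose of IMP | completion visit |
| Protocol v02, 3.1.2 | first dose of IMP | first dose of IMP | completion visit |

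Only the start of the denominator in 8.1 is out of line.

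**Inputs**

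- N = bleeds counted from the PK dose to completion.
- P = days of prophylaxis. The completion visit falls at 6 months (+2 weeks) after prophylaxis starts (Protocol 6.1.6), taken here as 183 to 197 days.
- g = days from the PK dose to the first prophylactic dose. The PK phase lasts 2 days (Protocol 5.4.1) and its last sample is at 48±2 h (Protocol 6.1.2), so g of about 2 is built into the schedule. No maximum is set, so larger values are assumptions.
- The completion visit takes place, and there is no surgery.

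**Formulas**

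- SAP 8.1: N × 365.25 / P
- SAP 5.7.2 and Protocol v02 3.1.2: N × 365.25 / (P + g)
- Ratio: (P + g) / P = 1 + g/P, so the relative excess is g/P whatever N is.

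**Relative excess of the 8.1 rate**

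| P (days) | g (days) | g/P |
|---|---|---|
| 183 | 2 | 1.09% |
| 183 | 3 | 1.64% |
| 183 | 7 (assumed) | 3.83% |
| 183 | 14 (assumed) | 7.65% |
| 197 | 2 | 1.02% |
| 90 (assumed withdrawal) | 2 | 2.22% |
| 30 (assumed withdrawal) | 2 | 6.67% |

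The last two rows matter because the full analysis set admits any enrolled child with one infusion after the PK Visit, so short follow-up can enter the analysis.

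**Absolute size at P = 183, g = 2**

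- One bleed: 365.25/183 = 1.996 against 365.25/185 = 1.974 per year, a difference of 0.022. If one child alone is affected, this moves a mean of 10 by 0.022/10 = 0.002 and an age-group mean of 5 by 0.022/5 = 0.004.
- Three bleeds: 5.988 against 5.923 per year, a difference of 0.065.

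**If a prophylaxis-only rate was intended**, the numerator is the part to change. A single bleed in the gap then scores 0 under a consistent definition, but 1 × 365.25/183 = 1.996 per year under 8.1.

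**The case against.** The strongest reply is that this is a wording alignment of little consequence. At the only gap the documents support, the excess is about 1%. The endpoints are secondary and descriptive with exploratory intervals, there is no hypothesis, and the error runs upward, against the product. Gaps of 7 or 14 days sit poorly with a schedule that hands over home treatment at the end of the PK Visit and normally doses every 2 to 3 days. All of this stands, and it limits the size of the point. It does not remove the conflict.

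Few bleeds are likely to be recorded in the gap: the child must not be bleeding at the PK dose, has just received 50 ± 5 IU/kg, and gets the diary only at the end of the visit. That is fair, but the excess does not need a bleed in the gap. Any bleed during follow-up is divided by the shorter time. Restricting the rate to documented periods (SAP 5.1.2, Protocol 9.2.4) does not bring the two start dates together either.

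Section 8.1 does not name the PK dose. Protocol 7.2.3 speaks of the bleeding rate under prophylactic treatment, so a prophylaxis-only window may have been meant. That reading is possible, but the same table uses different words for the first prophylactic treatment, and under that reading the numerator still has to be rewritten.

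No document ranks 8.1 above 5.7.2, and the sentence pointing to 8.1 sits in the paragraph on listings. This is a fair limit: that 8.1 would be the version programmed is a reasonable inference, not a certainty.

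Finally, the SAP title page also lists Protocol v03, which was not available, so the comparison with the protocol holds for v02 only. The conflict between 5.7.2 and 8.1 does not depend on it.

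**Conclusion.** The point holds. Section 8.1 states a rate whose events and time at risk start on different dates, and it contradicts 5.7.2 within the same SAP as well as Protocol v02 section 3.1.2. The mismatch is particular to SAP v1.2: versions 1.0 and 1.1 started the time at the first date of IMP.

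The expected effect is an excess of about 1%, on a 2-day gap and 6 months of prophylaxis. It is larger only with a late start of prophylaxis or early withdrawal, neither of which the documents predict. The result rests on the first dose of IMP being the PK dose, which follows from the design. This should be fixed because the contradiction is certain and the repair is nearly free, not because the study's conclusions are in danger.

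**What to change.** Use one start date for both count and time in SAP 8.1. There are two ways:

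- Start both at the first dose of IMP. This matches 5.7.2 and Protocol v02 section 3.1.2 and needs no declared departure from v02. One bleed with P = 183 and g = 2 then gives 1.974 per year.
- Start both at the first prophylactic injection. Then change 5.7.2 to match and declare the departure in SAP 3.2.

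Whichever is chosen, check it against Protocol v03.

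In the same edit, write the formula as 365.25 × N / days. As printed it has two successive division signs and no brackets; read left to right, one bleed in 183 days would give 1/183/365.25 = 0.000015 instead of 1.996. This is a bracket correction only, since 5.7.2 already expresses the duration in years.

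The cost is one derivation and matching wording. Protocol 7.2.2 already collects the date and time of each injection and the "Purpose of IMP injection (PK, IVR, prophylaxis, treatment of BE, surgery"), so either start date can be derived without new data.

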6.1.6 Study Completion (6-Month) Visit

The Study Completion Visit will take place 6 months (+2 weeks) after the start of the Prophylactic Treatment Phase.

A prophylactic injection of *Wilate* will be administered, if possible after a washout period of at least 48 hours from the patient's latest FVIII injection. Patients must not be experiencing any bleeding.

The following assessments will be performed:

- Review of patient diary
- Body weight before injection
- Blood samples will be taken for the following purposes and at the following time points:
 - FVIII:C plasma concentration (OS and CHR) for IVR assessment within 1 h
 before injection of the last prophylactic dose and 15±5 min after the end of the injection
 - Safety laboratory before and 15±5 minutes after injection
 - **FVIII inhibitor** before injection
 - Plasma VWF:Ag and VWF:Ac within 1 h before injection and 15±5 min after the end of injection
 - Parvovirus B19 antibodies before injection, if first sample was negative
- Vital signs before and 15±5 min after the end of injection
- AE monitoring
- Concomitant medication
- Physical examination

All used and unused IMP vials will be returned by the patient.

Patients prematurely withdrawing from the study for any reason will also be invited to attend the Study Completion Visit.

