5.3 IMP exposure, compliance

Treatment will be administered prophylactically as defined in the protocol. Each home treatment will be recorded in the diary along with the reason for treatment (prophylaxis, bleeding, prevention of recurrent bleeding, prophylaxis after surgery or other reason). Treatments in context of IVR and PK measurements and surgeries will be documented in the patients notes. All treatments, from diary or patient's notes, will be transferred into the eCRF.

All IMP treatment details will be listed.

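### SAP 8.1 divides prophylactic consumption by a period that, on its natural reading, also contains the PK window and any surgery phases

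*SAP*

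**What the plan says.** Protocol 3.1.2 lists as secondary endpoint 4 "Wilate consumption data (FVIII IU/kg per week per patient) for prophylaxis". SAP v1.2, section 5.7.2, carries it over as "consumption data (FVIII IU/kg per week and per month per subject) for prophylaxis". Neither section states a denominator.

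The denominator is in SAP v1.2, section 8.1, under *time under treatment*: "Date of last treatment – date of first treatment + 1", followed by the note that "average drug consumption data will be calculated relative to time under treatment". The entry makes no exception for prophylactic consumption and subtracts no surgery phases.

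The word treatment is used broadly. SAP 5.3 says "Treatments in context of IVR and PK measurements and surgeries will be documented in the patients notes" and sends all such entries to the eCRF. Protocol 5.4.1 places the PK dose before prophylaxis begins, and Protocol 6.1.2 starts the prophylactic phase at the first prophylactic injection after the PK Visit.

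The same table in SAP 8.1 also defines a *prophylactic treatment phase*. It starts at that first prophylactic injection and removes surgery phases, but the table applies it only to the annualized bleeding rates.

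**The concern.** A rate of prophylactic use should divide prophylactic doses by days on prophylaxis. Here the days between the PK dose and the first prophylactic dose, and the days of a surgery phase, stay in the denominator, while the endpoint's name implies that the doses given on those days are left out of the numerator. The result is a weekly figure that is too low, and lower in a child who had surgery than in an otherwise identical child who did not.

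With about 10 children, one distorted value is visible in the mean, the SD and the range. Readers will also set weekly consumption beside the bleeding rates to judge what dose intensity gave what control.

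**Working it through.** The documents give no figure on this point, so there is nothing to reproduce. The check applies the SAP 8.1 date formulas to an illustrative child.

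**Inputs**
- P = 183 days from first to last prophylactic dose, inclusive: an assumed day count for the 6 months in Protocol 5.4.2.
- g = days from PK dose to first prophylactic dose. The last PK sample is at 48 ± 2 h (Protocol 6.1.2) and the start of prophylaxis after it is not fixed. Assumed 2 or 3.
- s = length of the surgery phase. Not given; assumed 0, 1, 7, 14 or 21 days. For major surgery, Protocol 5.4.4 describes treatment until wound healing and then at least 7 more days.
- The numerator holds prophylactic doses only, given at a steady rate outside the surgery phase.

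**Formula.** Days on prophylaxis are P − s. Time under treatment is P + g. The dose cancels, so

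understatement = 1 − (P − s)/(P + g).

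| s (days) | g = 2 | g = 3 |
|---|---|---|
| 0 | 1 − 183/185 = 1.1% | 1 − 183/186 = 1.6% |
| 1 | 1 − 182/185 = 1.6% | 1 − 182/186 = 2.2% |
| 7 | 1 − 176/185 = 4.9% | 1 − 176/186 = 5.4% |
| 14 | 1 − 169/185 = 8.6% | 1 − 169/186 = 9.1% |
| 21 | 1 − 162/185 = 12.4% | 1 − 162/186 = 12.9% |

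**In units.** As an example inside the protocol's range, 30 IU/kg every 2.5 days is 30/2.5 × 7 = 84.0 IU/kg per week. With g = 2 the SAP denominator reports 83.1 without surgery, 79.9 with a 7-day phase, 76.7 with 14 days and 73.6 with 21 days.

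**On the group mean.** If one child in ten has a 14-day phase and all ten have the same true consumption, the mean is low by (9 × 1.1% + 8.6%)/10, or about 1.9%.

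**Dependence on the numerator.** If the PK dose of 50 IU/kg were counted (g = 2, no surgery), the example becomes (12 × 183 + 50)/185 × 7 = 85.0 IU/kg per week, 1.2% above 84.0. The direction reverses, and the figure is no longer consumption for prophylaxis.

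**A trap in the repair.** Protocol 7.2.2 records injection purpose with IVR and prophylaxis as separate categories, yet the 3- and 6-month IVR injections are prophylactic injections (Protocol 6.1.5, 6.1.6). A filter on purpose equal to prophylaxis could drop 2 of about 61 (183/3) to 91 (183/2) doses, or 2–3%. That is more than the PK-window error it was meant to remove.

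**The case against.** The SAP does not say that the first treatment is the PK dose, nor which doses are summed, so what is shown is an incomplete definition and not a demonstrated bias. The rule is worded for consumption in general, and SAP 5.7.2 also plans total consumption, for which first to last treatment is the right span. Without surgery the effect is 1–2%, against a permitted regimen that runs from 20/3 × 7 = 46.7 to 40/2 × 7 = 140 IU/kg per week. The endpoint is descriptive, surgery is incidental in this study, and all treatments are listed, so anyone can recompute.

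Most of this stands and sets the size of the point. The understatement is conditional on the numerator, and the rule should be kept for total consumption. It does not remove the point. SAP 5.3 and the order of visits make the PK dose the natural first treatment, the general rule is the only one given for endpoint 4, and a listing does not correct a prespecified summary.

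A reader might go further and infer that the bleeding-rate clock is wrong too. In SAP 8.1 it ends at "Date of completion visit or date of last treatment with IMP in case completion visit not performed", and Protocol 6.1.6 adds that "Patients prematurely withdrawing from the study for any reason will also be invited to attend the Study Completion Visit", so a withdrawn child may contribute days off Wilate. The documents do not support calling that an error. Protocol 3.1.2 itself runs the rate to the Study Completion Visit, which is compatible with a full analysis set described as intention-to-treat. Bleeds are counted to the same visit, so the direction of any effect is not fixed. Both documents also restrict the rates to documented periods; that does not remove documented off-treatment days, but it does exclude undocumented ones.

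Nor can the bleeding rates serve as a settled reference clock. SAP 5.7.2 and Protocol 3.1.2 start them at the first IMP dose, while the denominator in SAP 8.1 starts at the first prophylactic dose.

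**Conclusion.** The point holds for consumption only. On its natural reading, the stated denominator does not match an endpoint restricted to prophylaxis. With prophylactic doses alone in the numerator, weekly and monthly consumption are understated by about 1–2% in children without surgery and about 5–13% in children with a surgery phase of 7–21 days. These sizes rest on assumed values for the PK gap, the surgery length and a 183-day phase, and on an assumed numerator. No conclusion of the trial depends on them. It is a minor correction, worth making because it costs almost nothing and removes analyst discretion from a data set of about 10 children.

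**What to change.** In SAP 8.1, add an entry for endpoint 4:
- **Numerator:** prophylactic doses, including the 3- and 6-month IVR injections and excluding PK, bleed-treatment and surgery doses. State where the SAP 5.3 reasons *prevention of recurrent bleeding* and *other* fall.
- **Denominator:** date of last Wilate dose minus date of first prophylactic dose after the PK Visit, plus 1, minus surgery phases.

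Do not simply borrow the SAP's prophylactic treatment phase. For completers it ends on the same day, because a prophylactic injection is given at the completion visit, but for a withdrawn child it could add days off Wilate. Keep time under treatment as the denominator for total consumption of all doses.

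The cost is one definition and one reprogrammed summary. Dates, doses and purpose of each injection are already collected (Protocol 7.2.2). The bleeding-rate definition needs no change on this account; at most, a sensitivity analysis ending at the last dose could be shown for withdrawn children.
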